5.1.3 Subject Exclusion Criteria

The subject must be excluded from participating in the trial if the subject has:

1. Any condition or therapy impairing trial participation and assessments
2. The presence of a relapse or use of IV steroids for any reason 3 months prior to screening visit.
3. Severe systemic diseases or history of cancer or hereditary familiar cancer.
4. Clinically relevant concomitant disease: cardiac, gastrointestinal, hepatic, pulmonary, neurological, renal or other major disease.
5. Pregnant or breastfeeding women.
6. Drug or alcohol abuse.
7. Patients with active systemic bacterial, viral or fungal infections, or known to have AIDS or to test positive for HIV antibody at screening.
8. Ongoing known bacterial, viral or fungal infection (with the exception of onychomycosis and dermatomycosis), positive hepatitis B surface antigen or hepatitis C antibody tests at screening.
9. Patients with a known history of syphilis or tuberculosis or test positive for syphilis (positive rapid plasma regain, RPR) or tuberculosis (positive skin test) at screening.
Active or latent tuberculosis (TB).
10. Dementia or severe psychiatric, cognitive or behavioral problems or other comorbidity that may interfere with the compliance to the protocol.
11. Any other clinically relevant medical or surgical condition, which, in the opinion of the investigator, would put the subject at risk by participating in the study.
12. Participation in other experimental studies within the previous 90 days prior to screening visit.
13. Patients having a pacemaker or other metal implants.

5.2 Trial Treatment(s)

The investigator shall take responsibility for and shall take all steps to maintain appropriate records and ensure appropriate supply, storage, handling, distribution, and usage of trial treatments in accordance with the protocol and any applicable laws and regulations.

5.2.1 Therapeutic regimen Selection: tSCS stimulation protocols

The tSCS non-invasive spinal stimulation utilizes two modulated frequencies: (1) base frequency and (2) overlapping frequency. The base frequency is 30 Hz, whereby 1ms pulses are delivered 30 times per second (Figure 12 right). Within each pulse, an overlapping frequency of 10kHz is deployed to permit about 5-fold more current to be delivered for the same level of cutaneous sensation under the electrodes. This 10 kHz overlapping frequency is adapted from kilohertz-frequency muscle stimulation, permitting high-amplitude stimulation on the skin surface without discomfort. Thus, stimulation applied on the surface

of the skin can reach the spinal cord dorsal roots to activate spinal networks. The rationale for the 10 kHz overlapping frequency is that high-frequency waveforms can selectively block unmyelinated C-fibers in the skin^{6, 7}, and stimulation may penetrate more deeply due to the lowering of the tissue impedance ^{1, 8, 9}. We have observed substantial improvements in hand and arm function without inducing discomfort under the electrodes in our studies of more than 70 people with spinal cord injury^{1, 8, 10}.

[figure not shown]

Figure 12: (Left) SpineX device attached to two skin-surface electrodes for a child with cerebral palsy. (Right) Stimulation waveform with 10 kHz carrier frequency superimposed on each 1ms pulse, delivered 30 times per second to activate the spinal cord without discomfort from the surface of the skin.

Based on the protocol¹¹, stimulation waveforms are configured as monophasic or biphasic based on the configuration that leads to the most robust facilitation of arm and hand movements. The intensity of the stimulation is increased gradually (e.g., 5 mA steps) until the increase in muscle tone began to interfere with movement coordination or is judged uncomfortable by the participant. Treatment is performed with amplitudes of stimulation just below the motor threshold and adjusted as needed for the remainder of the therapy sessions as in prior studies^{1, 8, 10}.

5.2.2 Timing of Therapeutic Regimen Administration

The treatment will be administered 6 weeks in conjunction with standard occupational therapy.

5.2.3 Trial Blinding/Masking

Patient and physician will be blinded. For participants who randomize to the sham stimulation condition, the presence of active stimulation treatment will be concealed by using a sham stimulation that begins with the same stimulation waveforms and amplitudes used for treatment, but gradually reduces the stimulation current to zero over the first two minutes of each session. All participants will be instructed that they will most likely accommodate to the stimulation and not perceive it after several minutes. The treating researcher will be unaware of the patient allocation. An independent investigator informed of the therapeutic arm will prepare the device to administer treating stimulation or sham

and will record such assignment for each treating visit in a secured file not available for the treating researcher.

5.3 Randomization

Treatment allocation/randomization will occur centrally using an interactive voice response system / integrated web response system (IVRS/IWRS). There are 2 treatment arms: stim and sham. Subjects will be assigned randomly in a 1:1 ratio to either tSCS or sham.

5.4 Stratification

Randomization will be stratified by center.

5.5 Concomitant Treatments (Allowed)

Patients will be allowed to take their therapy prescribed for MS and any other comorbidity. Treatments specifically prohibited in the exclusion criteria are not allowed during the ongoing study. If there is a clinical indication for any treatment specifically prohibited during the trial, discontinuation from trial therapy may be required. The investigator should discuss any questions regarding this with the Principal Investigator. The final decision on any supportive therapy rests with the investigator and/or the subject's primary physician. However, the decision to continue the subject on trial therapy requires the mutual agreement of the investigator and the subject.

5.6 Rescue Treatments & Supportive Care

No rescue or supportive treatments are specified to be used in this trial.

5.7 Diet/Activity/Other Considerations

Not required.

5.7.1 Diet

Subjects should maintain their usual diet throughout the duration of the trial.

5.7.2 Use of Alcohol, Caffeine, and Tobacco

The site should advise subjects that alcohol should NOT be consumed during the study. The site should advise subjects to limit their alcohol intake as follows:

Refrain from consuming any alcohol for at least 24 hours prior to the study.

The site should advise subjects to limit their tobacco use as follows:

Refrain from the equivalent of >15 cigarettes a day during the study, and

Refrain from smoking during the study

5.7.3 Activity

NA

5.8 Subject Withdrawal/Discontinuation Criteria

Subjects may withdraw consent at any time for any reason or be dropped from the trial at the discretion of the investigator should any untoward effect occur. In addition, a subject may be withdrawn by the investigator if enrollment into the trial is inappropriate, the trial plan is violated, or for administrative and/or other safety reasons. Specific details regarding discontinuation or withdrawal procedures are provided in Section 7.1.4 – Other Procedures.

[Table 1](#) provides reasons why a subject must be discontinued from treatment but may continue to be monitored in the trial, as well as reasons why a subject must be discontinued from treatment and the trial.

Table 1 Discontinuation Scenarios

Reason for Discontinuation Scenario	Action
The subject or legal representative (such as a parent or legal guardian) withdraws consent.	Discontinuation from Treatment and Trial
The subject has a medical condition or personal circumstance which, in the opinion of the investigator, places the subject at unnecessary risk through continued participation in the trial or does not allow the subject to adhere to the requirements of the protocol.	Discontinuation from Treatment and Trial
The subject is no longer able to participate in the trial or is not compliant with trial-related procedures.	Discontinuation from Treatment and Trial
The subject takes a prohibited treatment during the trial.	This deviation should be documented and consulted regarding the management of the subject.
Subjects who report suicidal ideation with intent, with or without a plan or method (i.e., a positive response to items 4 or 5 in the assessment of suicidal ideation on the C-SSRS) or suicidal behavior may meet discontinuation criteria.	Please refer to Section 7.1.2.2.11, 7.2.3.2 and the ECI guidance document for details.

Discontinuation from treatment is “permanent.” Once a subject is discontinued, he/she shall not be allowed to restart treatment.

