7.1.1.2 Inclusion/Exclusion Criteria

If it is determined that the subject does not meet the inclusion/exclusion criteria at visits, the subject will be withdrawn from the study.

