7.1.2 Clinical Procedures/Assessments

7.1.2.1 Physical Assessments/Examinations

7.1.2.1.1 Neurological Examination (Neuro Exam)

A complete physical examination (PE), including a neurological exam, will be performed by a primary investigator or sub-investigator. This examination will also be performed in the event of early discontinuation. The following body systems should be included in these exams:

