7.1.4 Other Procedures

7.1.4.1 Withdrawal/Discontinuation

When a subject discontinues/withdraws from participation in the trial during visit 2 (before completing the three planned stimulations), all applicable activities scheduled for the end of visit 2, as outlined in Section 6.0 Trial Flow Chart, will be performed at the time of discontinuation. Any adverse events which are present at the time of discontinuation/withdrawal will be followed in accordance with the safety requirements outlined in Section 7.2 - Assessing and Recording Adverse Events

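### Table 1 and section 7.1.1.2 take randomised participants out of the trial for non-compliance or late-found ineligibility, and nothing requires their V5 9HPT

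*Protocol*

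**What the plan says.** Protocol 5.8 introduces Table 1 as covering, among other things, "reasons why a subject must be discontinued from treatment but may continue to be monitored in the trial". The table then lists five reasons. Consent withdrawal ends treatment and trial. So does a medical or personal circumstance that creates unnecessary risk or that "does not allow the subject to adhere to the requirements of the protocol". So does this row: "The subject is no longer able to participate in the trial or is not compliant with trial-related procedures". Taking a prohibited treatment leads to documentation and consultation, and suicidality is referred to other sections.

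The text above the table adds a discretionary power: "a subject may be withdrawn by the investigator if enrollment into the trial is inappropriate, the trial plan is violated". Section 7.1.1.2 is mandatory: "If it is determined that the subject does not meet the inclusion/exclusion criteria at visits, the subject will be withdrawn from the study".

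Two places deal with assessments on leaving early. Section 7.1.4.1 applies "When a subject discontinues/withdraws from participation in the trial during visit 2 (before completing the three planned stimulations" and calls for the end-of-visit-2 activities at the time of leaving. Section 7.1.2.1.1 says of the physical and neurological examination: "This examination will also be performed in the event of early discontinuation".

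Section 8.1 sets the primary test as the treatment-by-time interaction at the 6-week follow-up (V5) under intention to treat. It adds exploratory analyses in those who completed at least 70% of sessions. Section 5.9 rules out replacement.

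**The concern.** An intention-to-treat comparison needs outcomes from everyone randomised, whatever treatment they actually took. The protocol's withdrawal rules work against this. A participant who has not withdrawn consent can be removed for non-compliance, which is not defined, or for ineligibility that comes to light after randomisation. That participant's V5 9HPT then need not be collected, although the visit is already on the schedule.

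Non-compliance and stopping can depend on how treatment is going, whether through discomfort, lack of benefit or fatigue. The missing values may therefore be informative and may differ between arms. An analysis plan can model missing data but cannot supply a measurement that the protocol let go. The retention rate in 3.4, a stated safety and tolerability measure, would also count removals imposed by rule as losses.

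**Working it through.** **Timing of the primary outcome.** The flow chart (section 6.0) puts randomisation at Day 42. The double-blind period is 6 weeks: 42 + 6 × 7 = Day 84. This is the last of the double-blind assessment days listed and the V5 time point of section 8.1.

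**Table 1, row by row.**

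| Reason | Ends treatment and trial? | Must it? |
|---|---|---|
| Consent withdrawn | Yes | Yes |
| Medical or personal circumstance | Yes | Only where taking part is itself the risk |
| Unable to participate, or not compliant | Yes | Not for non-compliance alone |
| Prohibited treatment | No; documented and consulted | – |
| Suicidality | Referred elsewhere | – |

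Rows stating treatment-only discontinuation with follow-up: 0 of 5, although the introduction announces that category.

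**Ineligibility.** Randomisation happens at Visit 2 (7.1.1.9). The flow chart ticks the entry criteria at Visit 1 only, so no routine re-check after randomisation is planned. The gap is ineligibility discovered later. For that case 7.1.1.2 prescribes withdrawal from the study and 5.8 permits it; neither sets a cut-off at randomisation. Section 7.1.1.9 also speaks of screen failure at Visit 4. It stands between the sentence on randomising at Visit 2 and the one on all randomised subjects, so it is most likely a slip for Visit 2. Nothing here rests on it.

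**Does any other text secure the V5 value?**

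- 7.1.4.1 covers leaving during visit 2 only. The flow chart lists the 9HPT at Visit 2, so a 9HPT might be done, but at the stopping date and not at Day 84.
- 7.1.2.1.1 requires a physical and neurological examination, not a 9HPT.
- 7.1.5.1.3 places the 9HPT on the last day of stimulation in each session period. At best that again gives a value at the time of stopping.

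None requires it.

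**Room in the sample size (section 8.9).** The stated power reproduces: with 26 per arm, d = 4.4 / 5.5 = 0.8 and two-sided α = 0.05, two-sample t-test power is 80.7%, against the stated figure of above 80%.

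- Room for missing V5 outcomes: 60 − 52 = 8.
- The protocol's own attrition allowance: 0.15 × 60 = 9, leaving 51 (25.5 per arm), with power 80.0%.

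Removals under these rules may already lie within that allowance. The figures show only that there is little spare beyond it.

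**The case against.** The strongest reply has five parts.

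1. *A treatment-only stop exists elsewhere.* Section 5.5 says that if a prohibited treatment is indicated, "discontinuation from trial therapy may be required", and Table 1 sends that event to consultation. It is true that this concerns therapy and not the trial. It shows that the protocol knows the distinction, but it gives no follow-up rule and does not touch non-compliance.
2. *Non-compliance means not attending assessments.* On that reading V5 would often be unobtainable anyway, while missed sessions are handled through the attendance rate and the 70% set. The narrower reading is possible, and some non-compliers will decline V5. But the term is undefined, and 7.1.1.8 and 8.11 use compliance for treatment adherence. A 70% per-protocol set presupposes that low attenders stay in the trial, which sits badly with a row that can remove them.
3. *The medical row is a safety decision.* This stands for its risk limb. It does not stand for the limb about being unable to adhere.
4. *Section 7.1.1.2 is a screening rule.* Its position among the consent procedures and the Visit 1 tick support this. Its wording is nevertheless mandatory, refers to visits in the plural, and has no cut-off at randomisation.
5. *No harm is shown.* Section 8.1 does not drop removed participants, and the mixed model would use their earlier 9HPT values. Both points are right: intention to treat is not formally contradicted, and these participants are not wholly lost. Earlier values do not remove informative missingness at V5, where the primary contrast is made.

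**Conclusion.** The concern holds. Followed as written, the rules can remove randomised participants who have not withdrawn consent, and no text secures their V5 9HPT. That undermines the intention-to-treat primary comparison without formally contradicting it.

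The size cannot be stated. How many would be removed, and whether removal would differ by arm, is not known from the protocol, so no bias or loss of power is claimed. The conclusion rests on reading 7.1.1.2 and the non-compliance row as they stand, with no limit to before randomisation and no definition of compliance. It should be fixed before participants are lost, because the missing data cannot be recovered afterwards.

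**What to change.** - **5.8, Table 1:** make non-compliance, and any stopping of treatment without withdrawal of consent, a discontinuation from treatment only. State that the scheduled V5 (Day 84) 9HPT is still sought and that the participant is analysed as randomised. Keep exit from both treatment and trial for consent withdrawal and for cases where continued participation is itself unsafe.
- **7.1.1.2:** limit withdrawal for ineligibility to before randomisation. Record ineligibility found later as a protocol deviation, stop treatment if safety requires it, and continue follow-up.
- **5.8, text:** bring the sentence on inappropriate enrolment and plan violations into line with this.
- **7.1.1.9:** correct Visit 4 to Visit 2 (clerical).

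The cost is protocol wording and one already scheduled assessment for each participant who stops treatment. Safety is unaffected, since treatment can still be stopped at any time.

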5.9 Subject Replacement Strategy

No subject replacement is intended.

5.10 Beginning and End of the Trial

The overall trial begins when the first subject signs the informed consent form. The overall trial ends when the last subject completes the last study-related phone-call or visit, discontinues from the trial, or is lost to follow-up (i.e., the subject is unable to be contacted by the investigator).

5.11 Clinical Criteria for Early Trial Termination

There are no pre-specified criteria for terminating the trial early.

6.0 TRIAL FLOW CHART

Table 2 Trial flow chart

Visit Number	1	2	3-6	7
Visit Title	Screening	Randomization Baseline	Double blinded assessment	OLE

Scheduled Week/Day	Day 0	Day 42	Days 42-61-84	Day 126
Scheduling Window by Days:	±2	±3	±3	±5
Administrative Procedures				
Informed Consent – Subject	X			
Inclusion/Exclusion Criteria	X			
Subject Identification Card	X			
Medical History	X			
Prior Medication Review	X			
Randomization		X		
Monitor Trial Device Compliance		X		
Clinical Procedures/Assessments				
9HPT		X	X	X
ARAT		X	X	X
mAS		X	X	X
NeuroQOL		X	X	X
MFIS		X	X	X
GIC		X	X	X
Safety		X	X	X

7.0 TRIAL PROCEDURES

7.1 Trial Procedures

The Trial Flow Chart - Section 6.0 summarizes the trial procedures to be performed at each visit. Individual trial procedures are described in detail below. It may be necessary to perform these procedures at unscheduled time points if deemed clinically necessary by the investigator.

7.1.1 Administrative Procedures

7.1.1.1 Informed Consent

The investigator or qualified designee must obtain documented consent from each potential subject or each subject's legally acceptable representative prior to participating in a clinical trial. Documented consent from each subject (referred to as subject consent) will also be obtained by the investigator or qualified designee.

7.1.1.1.1 General Informed Consent

Consent will be documented by the subject's dated signature on a consent form along with the dated signature of the person conducting the consent discussion.

A copy of the respective signed and dated consent forms (subject consents) will be given to the subject and subject before participation in the trial.

The initial subject informed consent forms, any subsequent revised written informed consent forms and any written information provided to the subject will receive the Ethic Committee of the Hospital del Mar approval/favorable opinion in advance of use. The

subjects will be informed in a timely manner if new information becomes available that may be relevant to their willingness to continue participation in the trial. The communication of this information will be provided and documented via a revised consent form(s) or addendum to the original consent form(s) that captures the subject's dated signature.

Relevant clinical or MRI findings will be disclosed to the patient and refer for appropriate care.

Specifics about a trial and the trial population will be added to the consent form template(s) at the protocol level. Informed consent(s) will adhere to the ethics Committee requirements, applicable laws and regulations.

7.1.1.2 Inclusion/Exclusion Criteria

If it is determined that the subject does not meet the inclusion/exclusion criteria at visits, the subject will be withdrawn from the study.

7.1.1.3 Subject Identification Card

All subjects will be given a Subject Identification Card identifying them as participants in a research trial. The card will contain trial site (Hospital del Mar) contact information (including direct telephone numbers) to be utilized in the event of an emergency. The investigator or qualified designee will provide the subject with a Subject Identification Card immediately after the subject provides written informed consent.

7.1.1.4 Medical History

A medical history will be obtained by the investigator or qualified designee.

7.1.1.5 Prior and Concomitant Treatments Review

7.1.1.5.1 Prior Treatments

The investigator or qualified designee will review any prior therapeutic drug or neurostimulation use, in advance to visit 2, and record prior treatment taken by the subject within 30 days before starting the trial.

7.1.1.5.2 Concomitant Treatments

The investigator or qualified designee will record treatment(s), if any, taken by the subject during the trial. Any changes to treatment(s) (i.e., dose, frequency) will also be recorded. If the subject reports taking any prohibited treatments during the study, this will be recorded as a study deviation. Concomitant treatments will not be changed during the study, without first consulting the investigator, except in cases of medical emergencies or other obvious exceptions. Please see Section 5.5 for more details.

7.1.1.6 Assignment of Screening Number

All consented subjects will be given a unique screening number that will be used to identify the subject for all procedures that occur prior to randomization or treatment allocation. Each subject will be assigned only one screening number. Screening numbers must not be re-used for different subjects.

7.1.1.7 Assignment of Treatment/Randomization Number

All eligible subjects will be randomly allocated and will receive a treatment/randomization number. The treatment/randomization number identifies the subject for all procedures occurring after treatment allocation/randomization. Once a treatment/randomization number is assigned to a subject, it can never be re-assigned to another subject.

A single subject cannot be assigned more than 1 treatment/randomization number.

7.1.1.8 Trial Compliance (Treatment)

During stimulation visits, administration of tSCS therapy will be witnessed by the investigator and/or trial staff. Accounting of trial treatment will be conducted as specified in the Trial Flow Chart.

